Procedures:	Potential study participants will undergo a series of screening evaluations within 2 days prior to randomization. Subjects who give written informed consent and satisfy the selection criteria will be enrolled into the study. The temperature and SpO ₂ levels will be taken every 12 hours starting at baseline.
	Safety evaluations including assessment of adverse events (Days 1-21, Day 29, Day 45, and Day 60), 12-lead electrocardiogram (single) (baseline, Day 15, Day 22, and Day 29) and clinical laboratory results: urinalysis (baseline, Day 22, and Day 29), hematology (baseline, Day 3, Day 9, Day 15, Day 22, and Day 29), and serum chemistry (baseline, Day 3, Day 9, Day 15, Day 22 and Day 29).

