8.2 Enrollment

Enrollment should be done after the subject has completed the screening assessments and after it has been determined that the subject meets all the inclusion and exclusion criteria.

Subject will be randomized into one of two treatment groups.

8.3 Day 1

The Day 1 visit assessments will serve as the baseline assessments.

- 1. The medical history should be reviewed and updated to include any changes occurring since the screening visit. This will include the following:
 - a. Number of days from onset of COVID-19 symptoms to Day 1

- b. Specific reason for hospitalization
- 2. Assessment of eligibility
- 3. Vital signs (temperature/pulse/supine, if possible, blood pressure)
- 4. SpO_2
- 5. Physical examination (including weight)
- 6. Chest X-ray or Computed Tomography (CT) scan
- 7. Clinical Laboratory Tests
 - a. Hematology (Appendix A)
 - b. Serum chemistry (Appendix A)
 - c. Urinalysis
- 8. Record the usage of any concomitant medications and ongoing treatments.
- 9. Adverse events (ongoing on Day 1)
- 10. First dose of study drug
- 11. Temperature and SpO₂ every 12 hours after dosing

8.4 Day 2 through Day 21

The following assessments will be conducted on each of Day 2 to Day 21

- 1. Temperature and SpO₂ every 12 hours
- 2. Vital signs (temperature/pulse/supine, if possible, blood pressure)
- 3. Record the usage of any concomitant medications and ongoing treatments. This should include the following:
 - a. Documentation of the standard of care
 - b. The clinical rationale for initiation of mechanical ventilation, if necessary
 - c. Documentation of supportive measures for ARDS (e.g., proning, paralytics, etc.)
 - d. Care decisions that are based on limitations of resources at the clinical site
- 4. Adverse events
- 5. Dose study drug
- 6. At the time of discharge from the hospital, patients should be advised to use refrain from prolonged exposure to the sun or use at least SPF 50 on all exposed skin and protective clothing during prolonged sun exposure until the Day 60 adverse event assessment.

8.5 Day 3, Day 9, and Day 15

The following additional assessment will be conducted on Days 3, Day 9 and 15:

- 1. Serum Chemistry (Appendix A)
- 2. Hematology (Appendix A)
- 3. Assessment of primary and secondary endpoints (Day 15 only)
- 4. Physical examination (including weight) (Day 15 only)
- 5. 12 lead ECG (single) (Day 15 only)
- 6. Pregnancy test (Day 15 only)

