12.2 Appendix B: Schedule of Study Evaluations

Day	Screen ^a	Day 1	Days 2-21	Days 3, 9, & 15	Day 16	Days 22 ^d and 29	Days 45 and 60
Informed Consent and	Х						
HIPAA							
Medical History	Х	Х					
Assessment of Eligibility	Х	Х					
Physical Exam	Х	Х		Xf		Х	
Vital signs	Х	Х	Х			Х	
Pregnancy test (female	Х		Xf			X ^g	
subjects only)				0			
12-lead ECG (single)	Х			X ^t		X	
Chest X-ray or CT		Х				Х	
Clinical Laboratory Tests							
Hematology	Х	Х		Х		Х	
Urinalysis	Х	Х				Х	
Serum Chemistry	Х	Х		Х		Х	
Temperature/SpO ₂	Х	Х	Xe			Х	
Dosing ^{b,c}		Х	Х				
Pharmacokinetic assessment				X ^{h, f}	X ^h		
Assessment of primary and secondary efficacy endpoints				\mathbf{X}^{f}		Х	Х
Assessment of conmeds	Х	Х	Х			Х	
Assessment of AEs		Х	Х			Х	X

a Screening evaluations are to be conducted within 2 days prior to Day 1.

b Subjects will be treated for 21 days OR until discharged from hospital

c Subjects can be discontinued if they are not responding to therapy d Early termination assessments the same as Day 22 assessments

e Temperature and SpO₂ will be taken every 12 hours on these days

f Day 15 only g Day 29 only

h Plasma samples for pharmacokinetic assessment will be taken at baseline (prior to dosing on Day 15) and at 4 hours (±2 hours), 12 hours (±2 hours) after dosing on Day 15, and at 24 hours (±2 hours) after dosing on Day 15 (prior to dosing on Day 16).

PROTOCOL SIGNATURE PAGE

Protocol Number:	V0211901
Protocol Date:	FINAL Amendment 6 (Version 7)/ 25 September 2020
Protocol Title:	Randomized, Placebo-Controlled, Phase 2 Study of VERU-111 for the Treatment of Severe Acute Respiratory Syndrome Coronavirus 2 (SARS-CoV-2) in Patients at High Risk for Acute Respiratory Distress Syndrome (ARDS).

SIGNATURE:

Sponsor

Date

Name and Title of Sponsor Representative

This signature of the Sponsor Representative constitutes approval of this protocol.

PRINCIPAL INVESTIGATOR SIGNATURE PAGE

Protocol Number:	V0211901
Protocol Title:	Randomized, Placebo-Controlled, Phase 2 Study of VERU-111 for the Treatment of Severe Acute Respiratory Syndrome Coronavirus 2 (SARS-CoV-2) in Patients at High Risk for Acute Respiratory Distress Syndrome (ARDS).
Protocol Date:	FINAL Amendment 6 (Version 7)/ 25 September 2020

SIGNATURE:

Principal Investigator:

Date

Name of Principal Investigator (Please Print)

Address of Principal Investigator

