# 6.12.1 Primary Endpoint

QMD Ref: Worldwide-TMP-ST-005-7.0 Effective: 12Aug2019 Governing QMD: Worldwide-SOP-ST-		
Confidentiality Statement		
This document is the property of Worldwide Clinical Trials Inc. and may not be duplicated, copied, altered or removed from company without prior approval from Worldwide Quality Assurance or in compliance with Worldwide Standard Operating Procedures.		

REF: Worldwide-TMP-QA-001f-1.3

Worldwide Clinical Trials Controlled Quality Management Document		
WORLDWIDE CLINICAL TRIALS	Sponsor:	Veru Inc.
	Protocol Number:	V0211901
STATISTICAL ANALYSIS PLAN. PHASE 2-3-4		

The primary endpoint for the study is the proportion of subjects that are alive without respiratory failure at Day 29. Respiratory failure is defined as endotracheal intubation and mechanical ventilation, extracorporeal membrane oxygenation, high-flow nasal cannula oxygen delivery, noninvasive positive pressure ventilation, clinical diagnosis of respiratory failure with initiation of none of these measures only when clinical decision making is driven solely by resource limitation.

This analysis will compare the percentage of subjects that are alive without respiratory failure on Day 29 (responder).

Responders are subjects who have Grade 0-4 on the WHO Ordinal Scale for Clinical Improvement on Day 29. If subject was discharged from the hospital prior to Day 29 and WHO Ordinal Scale for Clinical Improvement is not collected at Day 29 then the last available observation before or at the time of discharge will be carried forward.

Non-responders are subjects who died before Day 29 or has Grade 5, 6, 7, or 8 on the WHO Ordinal Scale for Clinical Improvement on Day 29.

The number and percentage of responders will be summarized by treatment group. Responders will be analyzed using a logistic regression model. This model will include treatment as a factor, and study site, remdesivir use (No/Yes), dexamethasone use (No/Yes) and WHO Ordinal Scale for Clinical Improvement at baseline as a covariates. Odds ratios, standard errors, 95% confidence intervals and p-values for the treatment difference will be presented.

The primary analysis will be performed on the ITT population. A sensitivity analysis will be performed repeating the analysis on the EE population.

Example SAS code for the analysis is as follows:

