# 6.12.2.3 Proportion of subjects with normalization of fever and oxygen saturation through Day 15, Day 22, and Day 29.

The percentage of subjects with normalization of fever and oxygen saturation through Day 15, Day 22 and Day 29 (inclusive) will be summarized. A subject will be considered as a treatment success if fever normalization (body temperature < 37.0 °C) maintained for at least 24 hours AND peripheral capillary oxygen saturation (SpO2) >94% sustained for 24 hours is observed.

This analysis will compare the percentage of subjects that meet the composite endpoint at Day 15, Day 22, and Day 29.

Evaluation of the responder status will include all vital sign data and vital sign log data, and responder status will be evaluated at study days 15, 22 and 29 by checking if subject had normal temperature and SpO2 at least for the last 24 hours.

Responders are subjects who have fever normalization maintained for at least 24 hours AND peripheral capillary oxygen saturation (SpO2) >94% sustained for 24 hours is observed at the time of the visit.

Non-responders are subjects who died before the visit or do not meet both criteria of the endpoint (fever normalization and  $SpO_2>94\%$ ) at the time of the visit.

These endpoints will be analyzed using the same methodology as for the primary endpoint.

QMD Ref: Worldwide-TMP-ST-005-7.0 Effective: 12Aug2019 Governing QMD: Worldwide-SOP-ST-0		
Confidentiality Statement		
This document is the property of Worldwide Clinical Trials Inc. and may not be duplicated, copied, altered or removed from company without prior approval from Worldwide Quality Assurance or in compliance with Worldwide Standard Operating Procedures.		

Worldwide Clinical Trials Controlled Quality Management Document		
WORLDWIDE CLINICAL TRIALS	Sponsor:	Veru Inc.
	Protocol Number:	V0211901
STATISTICAL ANALYSIS PLAN. PHASE 2-3-4		

Separate analysis will be performed for each visit.

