### 6.15.3 Vital Signs

Descriptive statistics for observed values and changes from baseline in the following vital signs will be presented by treatment group and visit:

- Systolic blood pressure (mmHg)
- Diastolic blood pressure (mmHg)
- Pulse rate (bpm)
- Respiration rate (breath / min)
- Body weight (kg)
- Body temperature (degrees Celsius)
- SpO2 (%)

Vital Signs log will be collected every 12 hours during study days 1-21. When study day has more than one record then summary table will use the average within the day.

Data for body temperature and SpO2 log will be presented in plot where individual subjects will be overlaid in one figure (spaghetti plot) by treatment group.

All vital sign data will be listed.

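### The fever and oxygen-saturation endpoint needs 24 hours of readings that are not scheduled at Day 29, and the text supports competing outcomes for patients discharged without such readings (minor)

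*SAP*

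**What the plan says.** **The rule.** SAP 6.12.2.3 keeps the protocol's wording of normalization through each day, but its working rule looks back from the evaluation: "responder status will be evaluated at study days 15, 22 and 29 by checking if subject had normal temperature and" SpO2 over at least the last 24 hours, using all vital-sign and log data. Normal means a temperature below 37.0 °C and SpO2 above 94%. On failure it says "Non-responders are subjects who died before the visit or do not meet both criteria of the endpoint", and on method "These endpoints will be analyzed using the same methodology as for the primary endpoint". It does not mention discharge or absent readings.

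**The readings.**
- SAP 6.15.3: "Vital Signs log will be collected every 12 hours during study days 1-21".
- Protocol 8.4, whose list opens with 12-hourly temperature and SpO2: "The following assessments will be conducted on each of Day 2 to Day 21".
- Protocol Appendix B, footnote e: "will be taken every 12 hours on these days". The footnote is attached only to the Days 2-21 cell; the Day 22 and 29 column carries a plain mark.
- Protocol synopsis, Procedures: "levels will be taken every 12 hours starting at baseline". No end day is given.
- Protocol 8.6 and 8.7: vital signs and SpO2 are listed once at the Day 22 visit and once at the Day 29 visit, each with a window of 3 days either side.

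**Rules for absent data elsewhere.** For a patient discharged before Day 29, SAP 6.12.1 provides that if the WHO score "is not collected at Day 29 then the last available observation before or at the time of discharge will be carried forward". Protocol 9.3.1 instead excludes patients whose respiratory failure or vital status is unknown, with a sensitivity analysis counting them as non-responders. Protocol 9.4 leaves the detail on missing data to the SAP.

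**The concern.** There are two separate problems.

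First, a 24-hour look-back needs readings spread over 24 hours. If the 12-hourly log stops at Day 21, a Day 29 result rests on one reading and does not measure what the endpoint claims.

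Second, treatment ends at discharge, and neither document describes home readings. A patient who recovers and leaves before a visit may therefore have no 24-hour record at that visit. Read literally, such a patient does not meet both criteria and is a failure. That would count against whichever arm discharges patients sooner. Two programmers working from the same text could also produce tables whose differences point in opposite directions.

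**Working it through.** The documents give no target, rate or power figure for this endpoint, so there is no stated figure to reproduce.

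**Step 1. Do scheduled readings cover the look-back for an inpatient?** Inputs: log on Days 1-21 (SAP 6.15.3, protocol 8.4), one reading at each of the Day 22 and 29 visits, and the visit windows. Clock times are assumed: log at 08:00 and 20:00, evaluation or visit at 08:00 or 14:00.

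| Evaluation | Dates | Readings in last 24 hours | Covered |
|---|---|---|---|
| Day 15 | 15 | 3 | Yes |
| Day 22, visit on Days 19-22 | 4 of 7 | 2-3 | Yes |
| Day 22, visit on Days 23-25 | 3 of 7 | 1 | No |
| Day 29, visit on Days 26-32 | 7 of 7 | 1 | No |

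A Day 29 visit falls 26 - 21 = 5 to 32 - 21 = 11 days after the log ends. The Day 22 gap exists only if status is judged at the visit date. At study day 22 itself, the Day 21 readings fall within the look-back.

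**Step 2. What happens to a patient discharged alive without 24-hour readings?** Three outcomes can be argued:
- Non-response, from the literal text of SAP 6.12.2.3.
- Exclusion, from protocol 9.3.1 by way of the cross-reference in protocol 9.4.1.3. That rule concerns respiratory failure and vital status, and SAP 6.12.1 does not restate it.
- Carry-forward, from SAP 6.12.1 by way of its cross-reference. That rule is written for the WHO scale.

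**Step 3. How much can the choice matter?** All rates here are assumptions. Let
- d = share discharged by Day 15 (arms A and B);
- q = share normal among those not discharged, with deaths counted as not normal;
- r = share of discharged patients with normal 24-hour readings after discharge;
- f = share normal in the last 24 hours before discharge.

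Take q, r and f each equal across arms. Then:
- Non-response: rate = d·r + (1-d)·q, so the difference is (dA - dB)(r - q).
- Carry-forward: rate = d·f + (1-d)·q, so the difference is (dA - dB)(f - q).
- Exclusion, with no discharged patient having readings: q in each arm, so the difference is 0.

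With 20 per arm and d = 0.80 v 0.60 (16 v 12 patients):

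| Rule | q = 0.25 | q = 0.50 |
|---|---|---|
| Non-response, r = 0 | 5% v 10% (-5) | 10% v 20% (-10) |
| Non-response, r = 0.25 | 25% v 25% (0) | 30% v 35% (-5) |
| Non-response, r = 0.50 | 45% v 40% (+5) | 50% v 50% (0) |
| Exclusion (4 v 8 patients left) | 0 | 0 |
| Carry-forward, f = 0.75 | 65% v 55% (+10) | 70% v 65% (+5) |
| Carry-forward, f = 1 | 85% v 70% (+15) | 90% v 80% (+10) |

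With d = 0.70 v 0.60, non-response at r = 0 gives -2.5 to -5, and carry-forward gives +2.5 to +7.5 for f from 0.75 to 1. The sign reverses only when discharge rates differ and r < q < f.

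**Step 4. Equal discharge rates.** If r or f differs between arms, the rules can still disagree. Take d = 0.60, q = 0.25 and r = 0 in both arms, with f = 1.00 v 0.75. Non-response gives 0.40 × 0.25 = 10% in each arm, a difference of 0. Carry-forward gives 0.60 + 0.10 = 70% v 0.45 + 0.10 = 55%, a difference of +15.

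**Step 5. Against sampling error.** A shift of 5 to 15 points is 1 to 3 patients in 20. The Wald 95% half-width is 1.96 × √[pA(1-pA)/20 + pB(1-pB)/20]. It is 16 points for 5% v 10%, 22 for 10% v 20% or 90% v 80%, and 25 for 85% v 70%. None of these differences could be told from zero.

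**The case against.** The strongest reply is that little is broken. Day 15 lies inside the log, and so does study day 22. SAP 6.12.2.3 also admits all vital-sign data, and the synopsis sets no end to 12-hourly readings, so further readings may exist at Day 29. There is a default for patients without readings, namely non-response. Every rate above is assumed, and the endpoint is one of many secondary ones that SAP 6.12.4 treats as descriptive.

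Much of this stands, and it rules out several stronger readings that a reader might infer:
- *That all three visits lack readings.* The log gap is decisive only at Day 29.
- *That no rule exists at all.* The literal text supplies one. The defect is that competing rules can also be reached through the cross-references, and that the literal one counts recovered patients as failures.
- *That the ICU and ventilation sections (SAP 6.12.2.7 and 6.12.2.11), which class discharged patients as responders, show an inconsistency.* They do not. Discharge settles whether a patient is in the ICU or ventilated; it does not settle temperature or SpO2.

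What does not stand is the appeal to other Day 29 data. The synopsis gives no end day, but protocol 8.4, Appendix B and SAP 6.15.3 all stop at Day 21, and SAP 6.2.9 disregards unscheduled post-baseline assessments in tabulations.

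**Conclusion.** The point holds and is minor. At Day 29 the 24-hour criterion cannot be verified from scheduled data on any of the 7 permitted dates. This follows from the text alone. At Day 22 the gap is conditional on judging status at a visit on Days 23-25; at Day 15 there is none for inpatients.

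The treatment of patients discharged without 24-hour readings is ambiguous. The possible sign reversal rests on assumed unequal discharge rates, on r < q < f, and on r, q and f each being equal across arms. It shows what the choice of rule could do and does not forecast this trial's result. Nor should a reader infer that equal discharge rates make the choice harmless, since that also needs r and f to be equal between arms.

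A reader might also infer that the trial's main result is at risk. The documents do not support that: the primary endpoint has its own definition and discharge rule in SAP 6.12.1.

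**What to change.** Amend SAP 6.12.2.3 as follows.
1. Label Day 29 a single-reading result for all patients, and state how an absent reading is counted, or drop Day 29.
2. Evaluate Day 22 at study day 22 using the Day 21 log readings, and flag visits on Days 23-25 as not verified over 24 hours.
3. At Days 15 and 22, do not count patients discharged alive without 24-hour readings as failures by default. Carry forward their status over the last 24 hours of log readings before discharge, and treat any abnormal post-discharge reading as non-response. Add two sensitivity analyses, one counting these patients as non-responders and one excluding them. Deaths stay non-responders.
4. Reconcile the protocol synopsis with protocol 8.4 on when 12-hourly readings end.

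The cost is SAP wording and programming on data already scheduled. If the database is already locked, report this as a labelled additional analysis in the study report, which SAP section 6 allows with justification. There are two downsides: carry-forward assumes that patients stay normal after discharge, and Day 29 no longer measures 24-hour normalization.

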6.2 Selection Criteria

6.2.1 Inclusion Criteria

Subjects accepted for this study must:

- 1. Provide informed consent
- 2. Be able to communicate effectively with the study personnel
- 3. Aged ≥ 18 years

- 4. Severe Acute Respiratory Syndrome Coronavirus (SARS-CoV-2) infection confirmed by polymerase chain reaction (PCR) test
- 5. Patients at high risk for ARDS, with known comorbidities for being at high risk, such as, Asthma (moderate to severe), Chronic Lung Disease, Diabetes, Chronic Kidney Disease being treated with dialysis, Severe Obesity (BMI ≥40), 65 years of age or older, primarily reside in a nursing home or long-term care facility, or immunocompromised.
- 6. Peripheral capillary oxygen saturation (SpO₂) ≤ 94% on room air at screening. If patient is on oxygen therapy at the time of presentation for screening and the SpO₂ levels were ≤94% prior to introduction to oxygen therapy with proper documentation example EMT notes or ER/ED notes, then the patient is considered to have met this inclusion criterion. If patient is on oxygen therapy at the time of presentation for screening and the SpO₂ levels prior to introduction to oxygen therapy are unknown, the patient may be considered to have met this inclusion criterion if oxygen therapy is removed and the SpO₂ levels fall to ≤94%, then the patient is considered to have met this inclusion criterion. However, removal of the oxygen therapy should only be done if it is considered medically reasonable.
- 7. Subjects must agree to use acceptable methods of contraception
 - If subject is female or the male subject's partner could become pregnant, use acceptable methods of contraception from the time of the first administration of study medication until 6 months following administration of the last dose of study medication. Acceptable methods of contraception are as follows: Condom with spermicidal foam/gel/film/cream/suppository [i.e., barrier method of contraception], surgical sterilization (vasectomy with documentation of azospermia) and a barrier method {condom used with spermicidal foam/gel/film/cream/suppository}, the female partner uses oral contraceptives (combination estrogen/progesterone pills), injectable progesterone or subdermal implants and a barrier method (condom used with spermicidal foam/gel/film/cream/suppository))

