9.4.1 Secondary Endpoints

9.4.1.1 Mean change from baseline in WHO Ordinal Scale for Clinical Improvement at Day 15, Day 22 and Day 29

The mean change in WHO Ordinal Scale for Clinical Improvement from baseline to Day 22 and from baseline to Day 29 will be assessed.

The worst category recorded on Day -1 will be baseline and the worst category recorded on Day 22 and Day 29 of the study will be used in this analysis.

Descriptive statistics (n, mean, standard deviation, median, minimum and maximum) will be summarized for absolute values, and change from baseline by treatment group and visit.

Change from baseline will be analyzed using mixed model for repeated measures (MMRM) including treatment, visit and treatment-by-visit interaction as fixed effects and study site and WHO Ordinal Scale for Clinical Improvement at baseline as covariate. The resulting F-tests will be based on Kenward-Roger's adjusted degrees of freedom. Least squares means, standard errors, 95% confidence intervals and p-values for treatments and treatment differences at each visit will be presented.

9.4.1.2 Proportion of subjects that are Grade 5, 6, 7, or 8 on the WHO Ordinal Scale for Clinical Improvement at Day 15, Day 22, and Day 29

Proportion of subjects that are Grade 5, 6, 7, or 8 on the WHO Ordinal Scale for Clinical Improvement at Day 15, Day 22, and Day 29 will be assessed. This analysis will compare the percentage of subjects that have NOT progressed to a WHO Ordinal Scale for Clinical Improvement score of 5, 6, 7, or 8 (responder) on Day 15, Day 22 or Day 29. The worst category on each day of the study will be used in this analysis. The percentage of subjects that meet these criteria in each of the two treatment groups will be summarized and compared observationally and statistically.

This endpoint will be analyzed using the same methodology as for the primary endpoint.

9.4.1.3 Proportion of subjects with normalization of fever and oxygen saturation through Day 15, Day 22, and Day 29.

The percentage of subjects with normalization of fever and oxygen saturation through Day 15, Day 22 and Day 29 (inclusive) will be summarized. A subject will be considered as a treatment success if fever normalization maintained for at least 24 hours AND peripheral capillary oxygen saturation (SpO₂) >94% sustained for 24 hours is observed.

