#### 6.12.3.2 Oxygen Use

Oxygen use will be summarized by treatment group as shift (decrease, no change, increase) from baseline (last oxygen dose prior to the date of treatment start) at study days 3, 9, 15, 22 and 29. This information will be derived from concomitant medication data for oxygen.

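### The oxygen-saturation half of the fever/oxygen normalization endpoint has no room-air or support condition, so afebrile patients held above 94% by oxygen or a ventilator count as responders

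*SAP*

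**What the plan says.** **Entry (Protocol 6.2.1, criterion 6).** Saturation must be at most 94% "on room air at screening". Patients already on oxygen can qualify in two ways, and both rest on an off-oxygen value. In the first, the recorded "levels were ≤94% prior to introduction to oxygen therapy with proper documentation". In the second, where the earlier value is unknown, "the patient may be considered to have met this inclusion criterion if oxygen therapy is removed" and saturation then falls to 94% or lower.

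**Endpoint (Protocol 5.3.2 and 9.4.1.3; SAP 3.2 and 6.12.2.3).** Protocol 9.4.1.3 states: "A subject will be considered as a treatment success if fever normalization maintained for at least 24 hours AND peripheral capillary oxygen saturation" is above 94% for 24 hours. SAP 6.12.2.3 makes the first half exact, "fever normalization (body temperature < 37.0 °C) maintained for at least 24 hours", and requires for the second half "peripheral capillary oxygen saturation (SpO 2 ) >94% sustained for 24 hours is observed at the time of the visit". Non-responders are patients who died before the visit or missed either half. Responder status comes from the vital-sign data and the vital-sign log.

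**Oxygen use (SAP 6.12.3.2).** This is a separate exploratory shift table: "This information will be derived from concomitant medication data for oxygen". It is not linked to responder status.

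**The concern.** The entry criterion recognises that a reading on oxygen does not show a patient's underlying saturation. The endpoint meant to show recovery drops that distinction. Three consequences follow from the text.

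- A patient still dependent on support can be counted as normalized.
- A patient whose saturation is already corrected by support can meet the SpO2 half at baseline, before any treatment effect.
- A patient in respiratory failure by the trial's own definition can be a success here at the same visit.

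At stake is what the three reported comparisons (Days 15, 22 and 29) mean. They will carry odds ratios, confidence intervals and p-values, because the primary endpoint's methods are applied to them.

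**Working it through.** The plan gives no expected rate or power figure for this endpoint, so there is no figure to reproduce. The check is of the text, followed by an illustration on assumed rates.

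**Step 1: is a support condition stated anywhere?** None of the four endpoint definitions (Protocol 5.3.2 and 9.4.1.3; SAP 3.2 and 6.12.2.3) mentions room air, supplemental oxygen or ventilation. The 12-hourly SpO2 readings (Protocol 8.3, 8.4 and Appendix B) carry no such condition either. SAP 6.12.2.3 is a complete rule: it names the data source, the responders and the non-responders. The WHO score and oxygen records are not inputs, so a programmer following it could not exclude patients on support.

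**Step 2: can affected patients be in the trial?** Yes. Criterion 6 provides for patients already on oxygen. Protocol 6.2.2 admits WHO 5, and WHO 6 for less than five days.

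**Step 3: the two rules side by side.** Take a patient at Day 29 with temperature below 37.0 °C and SpO2 above 94% for 24 hours:

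| Support at Day 29 | Primary endpoint (SAP 6.12.1) | Normalization (SAP 6.12.2.3) |
|---|---|---|
| WHO 3, no oxygen | Responder | Responder |
| WHO 4, mask or nasal prongs | Responder | Responder |
| WHO 5, non-invasive ventilation or high-flow | Non-responder | Responder |
| WHO 6-7, ventilated | Non-responder | Responder |

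The conflict with the primary endpoint is confined to WHO 5-7. At WHO 4 there is no conflict, but the endpoint still does not distinguish recovery from support.

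**Step 4: illustration (all rates assumed).** Let p be the share alive who meet both halves off support, and let 10% die in each arm. Let a be the share of the remaining survivors who are counted as successes because support holds SpO2 above 94% and they are afebrile for 24 hours.

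Counted rate = p + a × (1 − p − 0.10)

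With p = 0.70 on VERU-111 and 0.50 on placebo, and the same a in both arms:

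| a | VERU-111 | Placebo | Difference |
|---|---|---|---|
| 0 | 0.70 | 0.50 | 20 points |
| 0.25 | 0.70 + 0.25 × 0.20 = 0.75 | 0.50 + 0.25 × 0.40 = 0.60 | 15 points |
| 0.5 | 0.70 + 0.5 × 0.20 = 0.80 | 0.50 + 0.5 × 0.40 = 0.70 | 10 points |
| 0.8 | 0.70 + 0.8 × 0.20 = 0.86 | 0.50 + 0.8 × 0.40 = 0.82 | 4 points |
| 1 | 0.90 | 0.90 | 0 |

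With equal mortality and equal a, the difference is 20 × (1 − a) points.

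The fever half limits a. If support holds half of these survivors above 94% but only half of those are afebrile for 24 hours, then a = 0.5 × 0.5 = 0.25 and the difference is 15 points, not 10. A value of a that reflects saturation alone therefore gives an upper bound on the dilution.

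**Step 5: unequal shares.** With no true difference (p = 0.50 in both arms, 10% dead), let a be 0.8 in one arm and 0.5 in the other. The rates are 0.50 + 0.8 × 0.40 = 0.82 and 0.50 + 0.5 × 0.40 = 0.70, a spurious 12 points in favour of the arm with the larger share. Swapping the shares reverses the sign.

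**The case against.** The strongest reply is that little depends on this endpoint. It fills items 8 to 10 of a 28-item list in SAP 3.2. SAP 6.12.4 treats all secondary endpoints as descriptive, and the study is an unpowered proof of concept. Its tables (14.2.3.1 and 14.2.3.2) are not marked for the preliminary analysis, and the Phase 3 decision described in the protocol summary rests on respiratory failure. All of this stands, and it limits the weight of the point.

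Second, oxygen and ventilator dependence appears elsewhere: in the primary endpoint at three visits, ventilation days and proportions, the WHO score and the oxygen shift table. The model also adjusts for baseline WHO score. This helps a careful reader but does not repair the endpoint. The other tables are not linked to its responder status, and a baseline covariate does not correct a misclassified outcome.

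Third, a reader might infer that the secondary objective goes unanswered. The documents do not support that. The objective speaks of normalization, the endpoint lists define it as SpO2 above 94% for 24 hours, and the SAP implements that wording. The primary endpoint itself accepts WHO 4 as success. Room air is a stricter reading than the one promised; the case for it rests on the entry criterion and on the WHO 5-7 conflict.

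Fourth, a change made now alters a definition after enrolment, since SAP Section 9 says all randomized subjects were treated. That is a reason to report both versions and document the change.

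**Conclusion.** The gap is real and can be confirmed from the text alone. The rule counts afebrile patients on any form of support as normalized, and at WHO 5-7 this contradicts the primary endpoint at the same visit. The effect is dilution if support-held successes are similar in the two arms, and bias in either direction if they are not.

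The size is unknown. The illustration rests on assumed success rates, equal 10% mortality and, in the main table, equal shares in both arms; read with a saturation-only share, it overstates the dilution.

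Two stronger inferences should be resisted. Criterion 6 provides for patients on oxygen only conditionally, so it does not show that many will be. The row where the difference vanishes needs every surviving off-oxygen failure to be both held above 94% by support and afebrile for 24 hours, which nothing in the documents suggests. The definition should be corrected; the primary analysis is unaffected.

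**What to change.** In SAP 6.12.2.3, and in the matching definitions in SAP 3.2 and Protocol 5.3.2 and 9.4.1.3, require SpO2 above 94% for 24 hours without supplemental oxygen or ventilatory support. Count as a non-responder any patient with:

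- an observed WHO score of 4-7 at the visit; or
- an oxygen record documented as running within the 24-hour window.

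Two safeguards are needed.

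- Use only oxygen dates actually recorded. SAP 6.2.4 can impute a missing stop date to the last clinic visit, which could falsely extend oxygen into the window.
- Do not assign failure from a WHO score carried forward from discharge. Under the carry-forward rule in SAP 6.12.1, a patient discharged at WHO 4 would otherwise fail at Day 29 without having been observed then.

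Report the present any-oxygen version alongside as a supportive row, and list the change in SAP Section 9.

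The cost is wording plus one derivation from WHO and oxygen records already collected. No new measurement is needed, and no patient has to come off oxygen for a test. The downsides are lower success rates and that patients on long-term home oxygen cannot succeed.
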